## **STUDY POPULATION AND TOTAL NUMBER OF SUBJECTS**

Patients of both sexes with advanced renal cell carcinoma will be included, who have received axitinib as second line or subsequent lines in accordance with the conditions approved for use in this disease.

The aim is to include two groups of patients: one with a long-term response to the drug (a group of patients progression-free for at least 9 months) compared to a group of patients who are refractory to the treatment (group of patients who show disease progression at the first assessment after the initiation of treatment).

The maximum possible number of patients will be included, progression-free at 9 months after the initiation of treatment. The ratio of long-term responders (PFS  $\geq$ 9 months) and primary refractory patients (PFS  $\leq$ 3 months) is estimated to be around 2:1.

During the study recruitment period, the participating sites may include all patients who meet the study’s inclusion criteria and who do not meet the study exclusion criteria. Given that this is an observational and exploratory study, no hypotheses have been established and the sample size will not be pre-determined.

In this study, the treatment with axitinib will have started before the enrolment of the patient, so the decision to treat and enrol these patients will be independent of the decision to carry out this study, and will depend exclusively on the clinical judgement of the responsible doctor.

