### **8.5. Sample size**

Given the low incidence of metastatic renal cell cancer, and thus the population to be included in the study, the number of patients expected to be included will be small, and it is expected that it will be around 60 patients. However, as it is an observational and exploratory study, no hypotheses were specified and, therefore, the calculations of the sample size are not applicable.

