### **4 HYPOTHESIS AND DECISION RULES**

The level of significance will be  $\alpha=0.05$  two-tailed in all the statistical inference tests. Adjustment by multiple comparisons is not planned.

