- Duration of first-line treatment:([0-3] months, [3-6] months, [6-9] months, [9-12] months,  $\geq 12$  months).
- Duration of first-line treatment: ( $\leq 9$ months,  $>9$  months).
- Duration of first-line treatment: ( $\leq 12$ months,  $>12$  months).
- Duration of first-line TKi treatment: ([0-3] months, [3-6] months, [6-9] months, [9-12] months,  $\geq 12$  months).

It will be calculated the duration of the first line, if the drug was only a TKi.

- Duration of first-line TKi treatment: ( $\leq 9$ months,  $>9$  months).
- Duration of first-line TKi treatment: ( $\leq 12$ months,  $>12$  months).
- Duration of the first TKI treatment:( [0-3] months, [3-6] months, [6-9] months, [9-12] months,  $\geq 12$  months).

It will be calculated the duration of the first treatment with a TKi, in 1st or later line (always after axitinib).

- Patients treated with a TKi previous to axitinib other than first. It will be analysed the number of patients with a TKi previous to axitinib, different from the first TKi received.

It will be analysed the duration of this treatment.

- Best response with the TKI received in the first-line (CR, PR, SD, DP)
- Best response with a TKi previous to axitinib with a TKi other than first line (CR, PR, SD, PD).
- Best response with line prior to axitinib with a TKI if a line prior to axitinib other than the first one has been received (CR/PR, SD, DP).
- Number of metastatic locations (1, 2 and  $\geq 3$ ); See this definition in section 7 Definitions of variables and objectives.
- Site of metastases (CNS metastases [yes vs no]; lymph nodes [yes vs no]; lung [yes vs no]; liver [yes vs no]; bone [yes vs no]). In addition to showing the descriptive and comparative table of metastatic locations between groups, another similar table will be shown but with the categories “Hepatic” and “Bone” united in a single.
- Neutrophil/lymphocyte ratio  $\leq 3$  (yes vs no). See this definition in section 7 Definitions of variables and objectives. It will be analysed in all moments included in the study.
- Line of treatment in which it was received.

- 
- Presence of comorbidities.
  - Suspension of treatment.
  - Have you received any further treatment?
  - Has there been disease progression?
  - Best response to treatment (RC, RP, EE, PE).
  - Best response to treatment (RC / RP, EE, PE).
  - Duration of axitinib treatment.
  - Vital status

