  - Baseline LDH levels  $>1.5 \times \text{ULN}$  (yes vs no). At the beginning of 1st line
  - Baseline Hgb levels  $\leq \text{LLN}$  (yes vs no). At the beginning of 1st line
  - Baseline corrected Ca++ levels  $>10$  mg/dl (yes vs no). At the beginning of 1st line
  - Baseline neutrophil levels  $> \text{ULN}$  (yes vs no). At the beginning of 1st line
  - Baseline platelet levels  $> \text{ULN}$  (yes vs no). At the beginning of 1st line
  - Smoking habits (smoker, non-smoker or former smoker). At the beginning of 1st line
  - Baseline LDH levels  $>1.5 \times \text{ULN}$  (yes vs no). At the beginning of axitinib treatment
  - Baseline Hgb levels  $\leq \text{LLN}$  (yes vs no). At the beginning of axitinib treatment
  - Baseline corrected Ca++ levels  $>10$  mg/dl (yes vs no). At the beginning of axitinib treatment
  - Baseline neutrophil levels  $> \text{ULN}$  (yes vs no). At the beginning of axitinib treatment
  - Baseline platelet levels  $> \text{ULN}$  (yes vs no). At the beginning of axitinib treatment
  - Smoking habits (smoker, non-smoker or former smoker). At the beginning of axitinib treatment

A logistic regression model will then be carried out to study the association between belonging to each of the two extreme treatment response groups, with each of the possible clinical factors of interest, prior to axitinib treatment. That is, those baseline factors (prior to the start with axitinib) that have been studied in section 7 and that are significant ( $P < 0.05$ ) or close to significance ( $P < 0.15$ ).

The factors in this situation will be summarized below, and that potential prognostic factors of the response to axitinib treatment (long responding group vs refractory group) are considered.

---

The optimal model of prognostic factors will be constructed with the variables that are finally significant ( $P < 0.05$ ).

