**Logistic regression:**

A logistic regression model will be used to study the association between membership to each of the two extreme treatment response groups with each of the possible clinical factors of interest (see the study factors in point 7.1. Primary objective).

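### The SAP's logistic model has no provision for zero cells: with about 40 v 20 patients, a factor that passes the screen can have an infinite odds ratio and, if retention uses a Wald P, be dropped however strong it is

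*SAP*

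**What the plan says.** SAP 7.1 lists the candidate factors, compares each between long-term responders and refractory patients, and takes into a logistic model those baseline factors that are significant (P<0.05) or "close to significance" (P<0.15). It then states: "The optimal model of prognostic factors will be constructed with the variables that are finally significant", with P<0.05 as the criterion.

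On the model itself, SAP 9.1 says: "A logistic regression model will be used to study the association between membership to each of the two extreme treatment response groups". The software is SPSS V18.0 or later. SAP 9.1 provides Fisher's exact test for contingency tables. For the model, the SAP does not mention penalised or exact estimation or zero cells, gives no rule for merging sparse levels, and does not say whether the retention P is Wald, score or likelihood-ratio.

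The list includes levels likely to be sparse. One item is "Site of metastases (CNS metastases [yes vs no", with four further sites; others are four-level histology, ECOG of 2 or more, and best response to the first-line TKI with complete response as its own level. Protocol 6.1.1 gives 5% as the background share of CNS metastases and about 80% as the clear-cell share.

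On size, Protocol 8.5 says "it is expected that it will be around 60 patients" and that "no hypotheses were specified and, therefore, the calculations of the sample size are not applicable". The Protocol abstract says the ratio of responders to refractory patients "is estimated to be around 2:1". SAP 8 substitutes no missing values other than incomplete dates.

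**The concern.** When every patient with a given factor level falls in one response group, the likelihood keeps rising as the coefficient grows and has no finite maximum. The fitted odds ratio and its standard error then depend on where the iterations stop. The Wald statistic is the ratio of the two and collapses towards zero, so its P approaches 1 even when the association is strong. A zero cell in one factor is enough to cause this in a multivariable model too.

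The study compares two extreme response groups in order to find strong contrasts, and a level present in only one group is the strongest contrast a table can show. It is also the case that the stated model cannot estimate. Under a Wald rule, it can be left out of the final model while a weaker factor stays in. Identifying factors associated with long-term response is part of the primary objective, and this model is where that analysis ends.

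**Working it through.** **Group sizes.** The plan has no power or sample-size figure to reproduce. Its expected 60 patients at 2:1 give 60/(2+1) = 20 refractory and 40 long-term responders.

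**What the fit does.** Compare two tables, written as responders v refractory patients with the level.

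*0/40 v 5/20*
- Fisher: C(20,5)/C(60,5) = 15,504/5,461,512 = 0.0028. The opposite tail is larger, so two-sided P=0.003.
- Maximum likelihood: log-odds coefficient about 22 and still rising after 20 iterations, SE about 18,000, Wald P=0.999.
- Likelihood ratio: null log-likelihood 20 ln(20/60) + 40 ln(40/60) = −38.19; fitted 15 ln(15/55) + 40 ln(40/55) = −32.23; twice the difference is 11.93, P=0.0006.
- Firth: with one binary factor this equals adding 0.5 to each cell, so OR = (5.5 × 40.5)/(15.5 × 0.5) = 28.7; penalised likelihood-ratio P=0.002.

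*1/40 v 5/20*
- Log odds ratio ln[(5 × 39)/(15 × 1)] = ln 13 = 2.565; SE = √(1/1 + 1/39 + 1/5 + 1/15) = 1.137; z = 2.256; Wald P=0.024.
- Fisher P=0.013.

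The first table is the stronger on Fisher's test, yet a Wald rule drops it and keeps the second. A likelihood-ratio rule keeps both, but the odds ratio and one confidence limit in the first remain infinite.

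**Zero cells before the screen.** For a level with the same prevalence p in both groups, P(zero cell in exactly one group) = a + b − 2ab, with a = (1−p)^20 and b = (1−p)^40. At p = 0.05, a = 0.358 and b = 0.129, giving 0.395. At 10% it is 0.13 and at 20% it is 0.01.

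**Zero cells after the screen.** SAP 7.1 admits only factors with P<0.15, so the relevant event is a zero cell together with passing that screen. All 40 v 20 binomial tables were enumerated, with chi-squared for the screen, or Fisher where an expected count was below 5. The last column requires Fisher P<0.05. All rates are assumptions, except that 5% matches the background CNS figure.

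| Rate, responders v refractory | Zero cell and P<0.15 | Zero cell and P<0.05 (a Wald rule drops it) |
|---|---|---|
| 5% v 5% (no association) | 3.5% | 1% |
| 5% v 20% | 12% | 10% |
| 30% v 5% | 35% | 34% |
| 2% v 20% | 41% | 35% |
| 20% v 2% | 48% | 38% |

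For four-level histology with no association and assumed splits from 70/10/10/10 to 80/10/5/5, simulation gives at least one zero cell in 36% to 69% of studies, and a zero cell plus a passed screen in about 9% to 12%.

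**Sensitivity to size.** The pre-screen figure for an unrelated 5% factor is 0.48 at N=45, 0.39 at 60, 0.24 at 90 and 0.14 at 120. Missing covariates move the usable count in the unfavourable direction.

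**The case against.** The strongest reply is that the screen removes most of the problem. A reader might infer from the 39.5% zero-cell figure that a factor such as CNS metastases will break the model in about four studies in ten. The SAP does not support that: an unrelated 5% factor reaches the model with a zero cell in only 3.5% of studies. Levels of about 20% or more with similar rates in both groups rarely produce a zero cell. This part of the reply stands. What remains is that the zero-cell factors that do get through are mainly those that look strongly associated.

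A reader might also infer that the plan will discard its strongest factor. The SAP does not name a Wald test, and a likelihood-ratio P would keep the factor. Ordinary maximum likelihood is itself an inference from the absence of any named alternative. So the discarding is conditional. The infinite odds ratio under maximum likelihood is not.

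Third, the factor would not vanish from the report. SAP 7.1 and 9.2 compare every baseline characteristic between groups, with Fisher's test available, and a standard error in the thousands is conspicuous. That also stands: the damage is confined to the logistic model.

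Finally, the study is exploratory, and 60 is an expectation with no cap. This lowers the severity, but a larger sample reduces the risk without removing it.

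**Conclusion.** The gap is real and modest in size. The SAP sets a P<0.05 retention rule for a logistic model at about 40 v 20 without saying how a zero cell is to be handled or which test supplies the P. A factor that passes the screen with a zero cell has no finite maximum-likelihood odds ratio. If the retention P is Wald, that factor is dropped whatever its strength.

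The risk that a given factor both passes the screen and has a zero cell is about 3.5% for an unrelated 5% factor, and 12% to 48% under the assumed associations. The risk that a Wald rule then removes a factor with univariable P<0.05 is 1% and 10% to 38% respectively. These figures rest on 60 patients at 2:1, on assumed factor rates, and on maximum likelihood as the inferred estimator. Severity is COULD to SHOULD.

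**What to change.** In SAP 7.1 and 9.1, state that the logistic models will be fitted by Firth's penalised likelihood with profile-likelihood confidence intervals, and that retention will use the penalised likelihood-ratio P, not a Wald P. In the 0/40 v 5/20 example this gives OR 28.7 and P=0.002, and the factor is kept.

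Keep the protocol's four histology categories in the tables. If levels are to be merged in the model, do so by a rule fixed without reference to response group that says where the two mixed categories go. A simple clear-cell/non-clear-cell split would leave that open.

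The cost is SAP wording and a routine outside basic SPSS. Estimates shrink slightly towards no effect. Intervals stay very wide when a cell is zero: for 0/40 v 6/20 the Firth odds ratio is 36 with a 95% interval from 3.9 to about 4,850. The method therefore gives a usable P value and a finite estimate, but little precision.

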## 7.2 SECONDARY OBJECTIVES

- Response to treatment with axitinib in the long-term responder group (defined as a PFS of at least 9 months with the drug). The "Best treatment response" variable from the "Treatment with axitinib" form will be analysed in this group of patients.
- Efficacy of axitinib by treatment line (second line treatment and further lines). Note: in treatments following axitinib, the "Date of progression" is not available, so times to progression will not be done.
  - o Treatment line in which axitinib is received (2,  $\geq 3$ ).

The following descriptive analyzes will be performed based on the treatment line on which axitinib has been received (2 vs.  $\geq 3$ ):

- o Best treatment response (CR, PR, SD, DP).
- o Duration of treatment.
- o Progression-free survival (this will not be performed for subsequent treatments).
- o Objective response rate (ORR) and clinical benefit (sum of CR, PR and SD).
- o Time to Progression (this will not be performed for subsequent treatments).
- o Overall Survival.
- Efficacy of axitinib per treatment line depending on the group (LR and Refractories)

A table will be displayed with the number of treatment line in which axitinib has been received in both groups of patients (2,  $\geq 3$ ). Depending on these groups (2,  $\geq 3$ ) the following analyzes will be performed in each of the groups (LR and PR):

- o Best treatment response (CR, PR, SD, DP).
- o Duration of treatment.
- o Progression-free survival
- o Objective response rate (ORR) and clinical benefit
- o Time to Progression
- o Overall Survival.

---

Likewise, a table will be shown with the number of patients with axitinib in the second line of treatment, and in  $\geq 3$  line in each group (long responders and refractories).

The following analyzes will be carried out by group (long responders / refractories):

- Best treatment response (CR, PR, SD, DP).
- Duration of treatment.
- Progression-free survival. PFS will be shown in all patients with axitinib in the second line of treatment, and PFS per group
- Objective response rate (ORR) and clinical benefit.
- Time to Progression
- Overall Survival. OS will be shown in all patients with axitinib in the second line of treatment, and OS per group
- Progression-free survival to sunitinib. PFS will be shown in all patients with axitinib in the second line of treatment, and PFS per group

It will be calculated as follows: Progression Free Survival to sunitinib (SLP, in months) = (Date of Progression of the Disease to treatment with sunitinib - Start date of treatment with sunitinib) / 30,4375. If there is no progression, the case is censored in SLP (months) = (Start date of treatment with axitinib - Start date of treatment with sunitinib) / 30,4375.

- **Majority sequence**

The number of patients receiving the second-line treatment will be shown, following the sequence that is most observed in all the patients included (SUT-AXI-NIVO).

The following analyzes will be carried out by group (long responders / refractories):

- Best treatment response (CR, PR, SD, DP).
- Duration of treatment (months).
- Progression-free survival. PFS will be shown in all patients with sunitinib-axitinib sequence and PFS per group.
- Objective response rate (ORR) and clinical benefit.
- Time to Progression
- Overall Survival. OS will be shown in all patients with sunitinib-axitinib sequence and OS per group
- Overall Survival since the beginning of 1st line. OS will be shown in all patients with sunitinib-axitinib sequence and OS per group

It is defined as: Global Survival from the beginning of the first line (SG, in months) = (Exit date - Start date of first line treatment) / 30,4375. If there is no exitus the case is censored in Global Survival (SG, in months) = (Date of last control - Start date of the first treatment) / 30,4375.

- To describe the duration of treatment with axitinib. It will be described as it is described in section 7. Definition of variables and objectives
- To describe the percentage of patients who had increase the dose of axitinib above 5 mg twice daily. It will be described as it is described in section 7. Definition of variables and objectives
- To describe the percentage of patients who had reduce the dose of axitinib below 5 mg twice daily. It will be described as it is described in section 7. Definition of variables and objectives
- To describe the tolerability of axitinib (see point 9.2. Statistical analyses, Safety objectives).
- To describe the response to treatments received at progression. The treatments received will be described in cases of DP for first-line, 2nd line, etc.; that is, in treatments prior to axitinib.
- Overall survival based on post treatment
  - o Overall survival. The OS will be displayed according to having received further treatment (Yes vs. No).
  - o The following analyzes will be carried out in the patient population depending on whether or not they have had subsequent treatment;
    - OS per group (LR vs RF).
    - OS per axitinib line (2 VS  $\geq 3$ ).
    - OS per group (LR vs RF) for patients with axitinib in line 2.
    - OS per group (LR vs RF) for patients with axitinib online  $\geq 3$ .
- Overall survival based on most recent subsequent treatment.

The following analyzes will be performed in this subpopulation of patients in the groups of patients who have had the 2 most common subsequent treatments:

- o OS
- o OS per group (LR vs RF)
- o OS per axitinib line
- o OS per group (LR vs RF) for patients with axitinib online 2
- o OS per group (LR vs RF) for patients with axitinib online  $\geq 3$
- To describe treatments received at progression. The treatments received in the cases of PD for first line, 2nd line etc ... it means, in the treatments previous to axitinib will be described. The analysis of post-axitinib treatments will be shown as explained in section 9.2 Statistical analysis.

The responses of the previous treatments to axitinib initiated by PD in the different registered lines will be presented.

